10.7. Appendix 7: ECG Findings of Potential Clinical Concern

ECG Findings That May Qualify as AEs

 Marked sinus bradycardia (rate <40 bpm) lasting minutes. New PR interval prolongation >280 msec. New prolongation of QTcF to >480 msec (absolute) or by \geq60 msec from baseline. New onset- atrial flutter or fibrillation, with controlled ventricular response rate: ie, rate <120 bpm. New onset type I second degree (Wenckebach) AV block of >30 seconds' duration. Frequent PVCs, triplets, or short intervals (<30 seconds) of consecutive ventricular complexes.
ECG Findings That May Qualify as SAEs

 QTcF prolongation >500 msec. New ST-T changes suggestive of myocardial ischemia. New onset left bundle branch block (QRS >120 msec). New onset right bundle branch block (QRS >120 msec). Symptomatic bradycardia. Asystole: 
 In awake, symptom free participants in sinus rhythm, with documented periods of asystole \geq3.0 seconds or any escape rate <40 bpm, or with an escape rhythm that is below the AV node. In awake, symptom free participants with atrial fibrillation and bradycardia with 1 or more pauses of at least 5 seconds or longer. Atrial flutter or fibrillation, with rapid ventricular response rate: rapid = rate >120 bpm. Sustained supraventricular tachycardia (rate >120 bpm) ("sustained" = short duration with relevant symptoms or lasting >1 minute).

- Ventricular rhythms >30 seconds' duration, including idioventricular rhythm (heart rate <40 bpm), accelerated idioventricular rhythm (HR >40 bpm to <100 bpm), and monomorphic/polymorphic ventricular tachycardia (HR >100 bpm (such as torsade's de pointes)).
- Type II second-degree (Mobitz II) AV block.
- Complete (third-degree) heart block.

ECG Findings That Qualify as SAEs

- Change in pattern suggestive of new myocardial infarction.
- Sustained ventricular tachyarrhythmias (>30 seconds' duration).
- Second or third-degree AV block requiring pacemaker placement.
- Asystolic pauses requiring pacemaker placement.
- Atrial flutter or fibrillation with rapid ventricular response requiring cardioversion.
- Ventricular fibrillation/flutter.
- At the discretion of the investigator, any arrhythmia classified as an adverse experience.

The enumerated list of major events of potential clinical concern are recommended as “alerts” or notifications from the core ECG laboratory to the investigator and Pfizer study team, and not to be considered as all-inclusive of what to be reported as AEs/SAEs.

10.8. Appendix 8: Protocol Amendment History

The Protocol Amendment Summary of Changes Table for the current amendment is located directly before the table of contents (TOC). The protocol amendment summary of changes tables for past amendment(s) can be found below:

Amendment 1 (01-October-2021)

Overall Rationale for the Amendment: This amendment is to enunciate details of clarifications [REDACTED] and statistical analysis.

Section # and Name	Description of Change	Brief Rationale
1.1 Synopsis: Objectives and Endpoints and [REDACTED] [REDACTED]	1. Removal of “%” from primary endpoint [REDACTED]	1. Typographic error, removed to avoid repetition [REDACTED]
1.1 Synopsis: Statistical Methods [REDACTED]	1. Replace “Baseline corrected TO” with “Percent TO” [REDACTED]	1. Clarification of primary [REDACTED] endpoint statistical methods

Section # and Name	Description of Change	Brief Rationale
2.2.1 Nonclinical Pharmacology	Addition of “RLK”	Clarification of TEC enzymes
5.2 Exclusion Criteria	
 1. Exclusion Criteria # 3, addition of “HIV” 2. Exclusion Criteria # 14, replace “90 days” with “30 days” 	
 1. Clarification of HIV screening as shown in SoA and Table 6 2. To facilitate subject recruitment for those with known participation in a clinical trial of ritlecitinib
8. Study Assessments and Procedures	Replace “350 mL” with “380 mL”	Update on blood volume required to accommodate JAK3 inhibition assay
8.4.2 Pharmacodynamics	
 1. Addition of section 8.4.2.1. for Target Occupancy assay 
CCI [REDACTED]
 
CCI [REDACTED]
 
CCI [REDACTED]
 
CCI [REDACTED]
 
CCI [REDACTED]
	For clarification of various pharmacodynamic assays
9.3.1 Primary Endpoints	
 1. Addition of “for each kinase” 2. Addition of “with TO_0 as the baseline variable of target occupancy, which is the mean of the two pre-dose measurements at Hour -1 and Hour 0 on Day 1. If only one of the two pre-dose measurements is available, TO_0 is 	Clarification of statistical methods for primary endpoint

Section # and Name	Description of Change	Brief Rationale
	
the available pre-dose measurement.”
 
3. Deleted “Baseline corrected”
	

CCI

10.1.11. Sponsor's Qualified Medical Personnel	
1. Delete “and (d) Pfizer Call Center number”2. Delete “The Pfizer Call Center number should only be used when the investigator and site staff cannot be reached. The Pfizer Call Center number is not intended for use by the participant directly; if a participant calls that number directly, he or she will be directed back to the investigator site”	Template modification
10.2. Appendix 2: Clinical Laboratory Tests	
1. Replaced “QuantiFERON TB Test” with QFT-G2. Replaced Interferon Gamma Release Assay with “IGRA”	To maintain consistency in the protocol

10.9. Appendix 9: Abbreviations

The following is a list of abbreviations that may be used in the protocol.

Abbreviation	Term
AA	alopecia areata
Abs	absolute
ADL	activities of daily living
AE	adverse event
ALC	absolute lymphocyte count
ALT	alanine aminotransferase
ANC	absolute neutrophil count
ARDS	acute respiratory distress syndrome
AST	aspartate aminotransferase
AUC	area under the curve
AUC ₂₄	area under the plasma concentration time profile from time 0 to 24 hours
AUC _{24,ss}	area under the plasma concentration time profile from time 0 to 24 hours at steady state
AUC ₄₈	area under the plasma concentration time profile from time 0 to 48 hours
AUC _{inf}	area under the plasma concentration time profile from time 0 extrapolated to infinity
AUC _{last}	area under the plasma concentration time profile from time 0 to the time of the last quantifiable concentration
AUC _{tau}	area under the plasma concentration-time profile from time 0 to time tau, the dosing interval
AV	atrioventricular
BA	bioavailability
BAEP	brainstem auditory evoked potential
BBS	Biospecimen Banking System
BCR	B cell receptor
BCRP	breast cancer resistance protein
BESP	bile salt export pump
β-hCG	beta human chorionic gonadotropin
BID	twice a day
BMI	body mass index
BMX	bone marrow tyrosine kinase gene in chromosome X
BP	blood pressure
BPM	beats per minute
BSEP	bile salt export pump
BTK	Bruton's tyrosine kinase
BUN	blood urea nitrogen
C _{av}	Average plasma concentration from time 0 to the time of the last quantifiable concentration

Abbreviation	Term
CD	cluster of differentiation
CFB	change from baseline
CFR	Code of Federal Regulations
CI	confidence interval
CIA	collagen induced arthritis
CIOMS	Council for International Organizations of Medical Sciences
CK	creatine kinase
CKD-EPI	Chronic Kidney Disease Epidemiology Collaboration
C_{last}	Plasma concentration at 48 hours post-dose
CL/F	apparent clearance
C_{max}	maximum observed concentration
C_{min}	minimum observed concentration
CMV	Cytomegalovirus
CNS	central nervous systems
CO ₂	carbon dioxide (bicarbonate)
COVID-19	coronavirus disease 2019
CRF	case report form
CRO	contract research organization
CRU	clinical research unit
CSR	clinical study report
CT	clinical trial
CTCAE	common terminology criteria for adverse events
CTMS	clinical trial management system
CYP	cytochrome P450
D	day
DDI	drug-drug interaction
DILI	drug induced liver injury
DMC	data monitoring committee
DNA	deoxyribonucleic acid
EBV	Epstein barr virus
EC	ethics committee
ECC	emergency contact card
ECG	electrocardiogram
eCRF	electronic case report form
EDB	exposure during breastfeeding
EDP	exposure during pregnancy
EFD	embryo-fetal developmental
eGFR	estimated glomerular filtration rate
EMA	European Medicines Agency
EPO	erythropoietin
ET	early termination

Abbreviation	Term
EU	European Union
EudraCT	European Clinical Trials Database
F	absolute oral bioavailability
Fa	fraction absorbed
FACS	fluorescence activated cell sorting
FIH	first in human
FSH	follicle stimulating hormone
GCP	Good Clinical Practice
GGT	gamma glutamyl transferase
GI	gastrointestinal
GLP	Good Laboratory Practice
HBcAb	hepatitis B core antibody
HBsAb	hepatitis B surface antibody
HBsAg	hepatitis B surface antigen
HCV	hepatitis C virus
HCVAb	hepatitis C antibody
HIV	human immunodeficiency virus
HR	heart rate
HRT	hormone replacement therapy
HS	hidradenitis suppurativa
HSV	herpes simplex virus
hWB	human whole blood
IB	investigator's brochure
IC ₅₀	50% inhibitory concentration
ICD	informed consent document
ICH	International Council for Harmonisation
IgD	Immunoglobulin D
IGRA	Interferon Gamma Release Assays
IL	interleukin
IMP	investigational medicinal product
IND	investigational new drug
INR	international normalized ratio
IP manual	investigational product manual
IPAL	Investigational Product Accountability Log
IQMP	Integrated Quality Management Plan
IR	immediate release
IRAK4	interleukin 1 receptor associated kinase 4
IRB	institutional review board
ITK	IL 2 inducible T-cell kinase
IUD	intrauterine device
IV	intravenous

Abbreviation	Term
JAK	Janus kinase
K ₂ EDTA	dipotassium ethylenediaminetetraacetic acid
LBBB	left bundle branch block
LFT	liver function test
LPLV	last participant last visit
MAD	multiple ascending dose
MATE	multidrug and toxin extrusion protein
MCH	mean corpuscular hemoglobin
MCHC	mean corpuscular hemoglobin concentration
MCV	mean corpuscular volume
CCI	
MMR	measles, mumps, and rubella combination vaccine
MR	modified-release
mRNA	messenger RNA
msec	milli-second
NADPH	nicotinamide adenine dinucleotide phosphate
N/A	not applicable
NK	natural killer
NOAEL	No-observed-adverse-effect level
OAT	organic anion transporter
OATP	organic anion transporting polypeptide
OCT	organic cation transporter
PBMC	Peripheral blood mononuclear cells
PCR	polymerase chain reaction
PCRU	Pfizer clinical research unit
PD	pharmacodynamic(s)
P-gp	P-glycoprotein
pH	potential of hydrogen
PK	pharmacokinetic(s)
PNS	peripheral nervous systems
PPD	purified protein derivative
PR	PR interval
PT	prothrombin time
PTR	peak-to-trough ratio
PVC	premature ventricular contraction/complex
QD	once daily
QFT-G	QuantiFERON Gold-TB test
QID	4 times a day
QRS	QRS interval
QTc	corrected QT
QTcF	corrected QT (Fridericia method)

Abbreviation	Term
qual	qualitative
RA	rheumatoid arthritis
RLK	resting lymphocyte kinase
RBC	red blood cell
RNA	ribonucleic acid
SAD	single ascending dose
SAE	serious adverse event
SAP	statistical analysis plan
SARS-CoV-2	severe acute respiratory syndrome coronavirus 2
SCr	serum creatinine
SoA	schedule of activities
SOC	system organ class
SOP	standard operating procedure
SRSD	single reference safety document
CCI	
SULT	sulfotransferases
SUSAR	suspected unexpected serious adverse reaction
$t_{1/2}$	half-life
TB	tuberculosis
TBili	total bilirubin
TBNK	T cell, B cell, natural killer cell
TCR	T cell receptor
TEAE	treatment emergent adverse event
TEC	tyrosine kinase expressed carcinoma
THC	tetrahydrocannabinol
TK6	thymidine kinase-6
TLR	toll-like receptor
T_{max}	time for C_{max}
TO	target occupancy
TO_{max}	maximum target occupancy
TXK	tyrosine kinase expressed in T cells
TYK	tyrosine kinase
UC	Ulcerative colitis
UDP	glucuronosyltransferase
UGT	glucuronosyltransferase
ULN	upper limit of normal
US	United States
VZV	Varicella zoster virus
WBC	white blood cell
WOCBP	woman/women of childbearing potential

## 1. VERSION HISTORY

**Table 1. Summary of Changes**

Version/ Date	Associated Protocol Amendment	Rationale	Specific Changes
1 18 Oct 2021	Protocol Amendment 1 01 Oct 2021	N/A	N/A

## 2. INTRODUCTION

*Ritlecitinib (previously known as PF-06651600) is a potent, covalent, and irreversible inhibitor of JAK3 with high selectivity over the other three JAK isoforms (JAK1, JAK2, and TYK2. Ritlecitinib also inhibits irreversibly the TEC family kinases BTK, BMX, ITK, RLK, and TEC) with selectivity over the broader human kinase. Ritlecitinib is being developed for the treatment of UC, CD, AA, RA, and vitiligo.*

*Inhibition of JAK3 by ritlecitinib is expected to modulate  $\gamma$ -common chain cytokine pathways, such as IL-7, IL-9, IL-15, and IL-21, but expected to spare inhibition of other JAK-dependent pathways that do not utilize JAK3, including IL-6 signaling and key immuno-suppressive cytokines, such as IL-10, IL-27 and IL-35. Selective JAK3 targeting may reduce adverse effects from other JAK pathways, including cytopenia's (JAK2 dependent), cardiovascular events, malignancies, and severe infections. Inhibition of TEC kinases by ritlecitinib is expected to modulate T cell and B cell development and function (TEC kinases are activated downstream of the TCR and BCR). These effects by ritlecitinib on TCR signaling have been shown to inhibit the cytotoxic function of CD8+T cells and NK cells. There is limited information on the degree of target occupancy by Ritlecitinib on JAK3 and TEC kinases (ie, irreversible kinase binding) in humans, and how TO and target turnover of both JAK3 and TEC kinases a) is regulated by drug half-life, and b) how TO translates into functional effects on specific cell types and pathways.*

*TO of JAK3 and the five TEC kinases by ritlecitinib has been demonstrated *in vivo* in NOD scid IL2r $\gamma$ -null mice engrafted with human PBMCs which expresses JAK3 and TEC kinases. Despite the large variation in occupancy measurements likely due to differing levels of human PBMC engraftment and the small number of mice (n=3) per time point, approximately 100% occupancy of JAK3 and most of the TEC kinases, except RLK, was observed in the spleen samples from early time points (0.25 to 5 h). A slower recovery of unbound BTK was seen compared to JAK3 and ITK due to relatively longer half-life of BTK (12-24 hours vs. 2-3 hours for JAK3/ITK). Since the PK profile of ritlecitinib is characterized by rapid absorption and rapid elimination half-life, it is important to study the relationship between TO of JAK3 and the TEC kinase family and the functional consequences of their inhibition over time by ritlecitinib in healthy participants to provide insights in assessing the impact in patients with inflammatory and autoimmune diseases. Based on the predicted PK for ritlecitinib, along with the need to assess target occupancy (and functional inhibition) in*

*a predefined specimen collection window, at least 2 doses would be required to capture expected concentrations in patients at clinically relevant doses and also to better understand the expected hysteresis in exposure and response.*

This statistical analysis plan (SAP) provides the detailed methodology for summary and statistical analyses of the data collected in Study B7981045. This document may modify the plans outlined in the protocol; however, any major modifications of the primary endpoint definition or its analysis will also be reflected in a protocol amendment.

## 2.1. Study Objectives, Endpoints, and Estimands

Objectives	Endpoints
Primary:	Primary:

 
• To characterize the TO of JAK3 and TEC kinases in peripheral blood mononuclear cells (PBMCs) after single oral dose of ritlecitinib
 
	
 
• Percent TO for JAK3 and TEC kinases (BTK, ITK, RLK, TEC and BMX)
 

Secondary:	Secondary:

 
• To evaluate the plasma exposure of ritlecitinib over 48 hours after single oral dose administration
 
• To evaluate the safety and tolerability of an oral dose of ritlecitinib when administered alone and in healthy adult participants
 
	
 
• Ritlecitinib plasma PK parameters 
 
• <math>C_{max}</math>, <math>T_{max}</math>, <math>C_{last}</math>, <math>C_{av}</math>, <math>AUC_{last}</math> and, <math>AUC_{24}</math>
 
 
 
• Assessment of TEAEs, clinical laboratory tests, and vital signs
 

Tertiary:	Tertiary:

 
• To characterize the relationship between TO in PBMCs and plasma ritlecitinib exposure over 48 hours after single oral dose
 
	
 
• Maximal inhibition (occupancy) by ritlecitinib (<math>TO_{max}</math>)
 
• Ritlecitinib plasma concentrations at 50% <math>TO_{max}</math> (<math>IC_{50}</math>)
 

[figure not shown]
CCI

## 2.2. Study Design

*This is a Phase 1, single dose, open label, two-arm study to assess TO of JAK3 and TEC kinases by ritlecitinib in healthy adult participants. A total of approximately 16 healthy male and/or female participants, 8 in each cohort, will be enrolled and dosed to achieve at least 6 participants completing each dose level. Participants who discontinue from the study for non safety reasons may be replaced at the sponsor's discretion.*

*Participants will be enrolled to receive either 50 mg or 200 mg single dose of ritlecitinib on Day 1 (See Figure 1). Blood samples to assess ritlecitinib PK, target occupancy and functional assays will be collected over 48 hours. Participants will remain in the CRU until Day 3 when they will be discharged after completion of study related activities as indicated in the SoA.*

**Figure 1. Study Schema**

### **3. ENDPOINTS AND BASELINE VARIABLES: DEFINITIONS AND CONVENTIONS**

#### **3.1. Primary Endpoint(s)**

The primary endpoint in human PBMCs is TO of JAK3 BTK, ITK, RLK, TEC and BMX after a single dose of ritlecitinib. Target occupancy for each kinase at time  $t$  will be evaluated as follows:

$$\% \text{ Target Occupancy}_t = 100 \% - \% \text{ Free Target}_t$$

with  $TO_0$  as the baseline variable of target occupancy, which is the mean of the two pre-dose measurements at Hour -1 and Hour 0 on Day 1. If only one of the two pre-dose measurements is available,  $TO_0$  is the available pre-dose measurement. (see [Section 3.4](#)).

#### **3.2. Secondary Endpoint(s)**

##### **3.2.1. PK Parameters**

*The secondary endpoints are pharmacokinetic parameters of ritlecitinib after single oral dose. PK parameters will be derived, given available data, following single dose administration from the concentration-time profiles for ritlecitinib as follows:*

**Table 2. Plasma PK Parameters**

Parameter	Definition	Method of Determination
$AUC_{24}$	Area under the plasma concentration-time curve from time 0 to 24 hours	Linear/Log trapezoidal method
$AUC_{last}$	Area under the plasma concentration-time curve from time 0 to the time of the last quantifiable concentration (<math>C_{last}</math>)	Linear/Log trapezoidal method
$C_{av}$	Average plasma concentration from time 0 to the time of the last quantifiable concentration	$AUC_{24}/24$
$C_{max}$	Maximum plasma observed concentration	Observed directly from data
$C_{last}$	Plasma concentration at 48 hours post-dose	Observed directly from data
$T_{max}$	Time to reach <math>C_{max}</math>	Observed directly from data as time of first occurrence

### 3.3. Other Endpoint(s)

#### 3.3.1. Tertiary Endpoints

CCI

Maximal target occupancy by ritlecitinib ( $TO_{max}$ ) and Ritlecitinib plasma concentrations at 50%  $TO_{max}$  ( $IC_{50}$ ) will be derived, if data permit.

### 3.4. Baseline Variables

Baseline TO, CCI will be defined as the mean of the two pre-dose measurements at Hour -1 and Hour 0 on Day 1. If only one of the two pre-dose measurements is available, the baseline will be defined as the available pre-dose measurement.

In general, for all other analyses, baseline will be defined based on observations collected prior to first dose. Baseline values for demographics, medical and other history will be based on measures collected at Visit 1/Screening visit. Study Day 1 is defined as the day the subject receives first dose of study drug. For purposes of all other analyses including analyses for change from baseline, the baseline value will be defined as measured on Day 1 pre-dose. If a value is missing on Day 1, then the last available observation before Day 1 will be used.

### **3.5. Safety Endpoints**

The following data are considered in standard safety summaries (see protocol for collection days, baseline assessment, and list of parameters):

- AEs;
- clinical laboratory tests;
- vital signs;
- ECG.

#### **3.5.1. Adverse Events**

An adverse event (AE) is considered a Treatment-Emergent Adverse Event (TEAE) if the event started during the effective duration of treatment. All events that start on or after the first dosing day and time/start time, if collected, but before the last dose plus the lag time, will be flagged as TEAEs. The lag time is defined by the Pfizer Standard of 365 days post last dose of Ritlecitinib. The algorithm will not consider any events that started prior to the first dose date. If an AE starts on the same day as the first dose date, it will be considered treatment emergent unless the CRF data indicates otherwise via explicitly recording time for AE onset which was occurred before the first treatment dosing.

#### **3.5.2. Laboratory Data**

Safety laboratory tests will be performed as described in the protocol.

To determine if there are any clinically significant laboratory abnormalities, the haematological, clinical chemistry (serum) and urinalysis safety tests will be assessed against the criteria specified in the sponsor reporting standards. The assessment will not take into account whether each subject's baseline test result is within or outside the laboratory reference range for the particular laboratory parameter.

Baseline of safety laboratory tests is defined as the pre-dose measurement on Day -1.

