2.3.1. Risk Assessment

Potential Risk of Clinical Significance	Summary of Data/Rationale for Risk	Mitigation Strategy
Study Intervention: Ritlecitinib		
1. Potential risks associated with study intervention include the following: a. transient decrease in leukocyte and platelet counts.	1. The potential risks are based on prior studies for ritlecitinib in healthy participants and RA, AA and vitiligo patients. Details are presented in the IB.	1. Eligibility criteria and study assessments have been selected to ensure that only appropriate participants are included in the study (see Section 5).
Other		
The COVID-19 pandemic may pose risks to study participation.	Participants may have increased risk of SARS-CoV-2 infection by undergoing a study procedure at a study facility.	Inclusion of COVID-19 specific assessments according to the Schedule of Activities and CRU confinement for the entire duration of study.

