Prior/Concurrent Clinical Study Experience:

13. Previous administration with an investigational drug within 30 days (or as determined by the local requirement) or 5 half-lives preceding the first dose of study intervention used in this study (whichever is longer).
14. Known participation in a clinical trial of ritlecitinib within 30 days prior to the first dose of study medications.
15. Known participation in a clinical trial of ritlecitinib and participant experienced treatment-related adverse events that led to discontinuation or an SAE (\geq CTCAE Grade 3).

Diagnostic Assessments:

16. A positive urine drug test.
17. Screening supine BP \geq 140 mm Hg (systolic) or \geq 90 mm Hg (diastolic), following at least 5 minutes of supine rest. If BP is \geq 140 mm Hg (systolic) or \geq 90 mm Hg (diastolic), the BP should be repeated 2 more times and the average of the 3 BP values should be used to determine the participant's eligibility.
18. Baseline standard 12-lead ECG that demonstrates clinically relevant abnormalities that may affect participant safety or interpretation of study results (eg, baseline QTcF interval $>$ 450 msec, complete LBBB, signs of an acute or -indeterminate age myocardial infarction, ST-T interval changes suggestive of myocardial ischemia, second- or third degree- AV block, or serious bradyarrhythmias or tachyarrhythmias). If the baseline uncorrected QT interval is $>$ 450 msec, this interval should be -rate corrected using the Fridericia method and the resulting QTcF should be used for decision making and reporting. If QTcF exceeds 450 msec, or QRS exceeds 120 msec, the ECG should be repeated 2 more times and the average of the 3 QTcF or QRS values should be used to determine the participant's eligibility. Computer-interpreted ECGs should be overread by a physician experienced in reading ECGs before excluding a participant.
19. Participants with **ANY** of the following abnormalities in clinical laboratory tests at screening, as assessed by the study-specific laboratory and confirmed by a single repeat test, if deemed necessary:
 - AST **or** ALT level $1.5 \times$ ULN;

- Total bilirubin level $\geq 1.5 \times$ ULN; participants with a history of Gilbert's syndrome may have direct bilirubin measured and would be eligible for this study provided the direct bilirubin level is \leq ULN.
- Hemoglobin level ≤ 135 g/L (13.5 g/dL) for males and ≤ 120 g/L (12.0 g/dL) for females.

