- Platelet count $\leq 100 \times 10^9$ /L (100,000 cells/mm³) or $\geq 1000 \times 10^9$ /L (1,000,000 cells/mm³).
- WBC count $\leq 3.0 \times 10^9$ /L (3000 cells/mm³) or ANC < 1500 cells/mm³ or ALC < 800 cells/mm³.
- eGFR ≤ 60 mL/min/1.73m² based on CKD-EPI equation.

Other Exclusions:

20. History of alcohol abuse or binge drinking and/or any other illicit drug use or dependence within 6 months of Screening. Binge drinking is defined as a pattern of 5 (male) and 4 (female) or more alcoholic drinks in about 2 hours. As a general rule, alcohol intake should not exceed 14 units per week (1 unit = 8 ounces (240 mL) beer, 1 ounce (30 mL) of 40% spirit or 3 ounces (90 mL) of wine).
21. Blood donation (excluding plasma donations) of approximately 1 pint (500 mL) or more within 60 days prior to dosing.
22. History of sensitivity to heparin or heparin-induced thrombocytopenia.
23. Unwilling or unable to comply with the criteria in the [Lifestyle Considerations](#) section of this protocol.
24. Investigator site staff or Pfizer employees directly involved in the conduct of the study, site staff otherwise supervised by the investigator, and their respective family members.

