#### **6.2.2.2. Laboratory Data**

Laboratory data will be listed and summarized by dose in accordance with the sponsor reporting standards. The baseline measurement is the pre-dose measurement on Day -1.

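### The laboratory abnormality count ignores baseline, so it can mix values already abnormal before dosing with new ones; a split by Day -1 status would cure this cheaply

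*SAP*

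**What the plan says.** Clinical laboratory tests are part of a secondary endpoint (Protocol 3; SAP 2.1). SAP 3.5.2 says that haematology, chemistry and urinalysis results "will be assessed against the criteria specified in the sponsor reporting standards" and then sets the rule at issue: "The assessment will not take into account whether each subject's baseline test result is within or outside the laboratory reference range". The same section fixes a baseline: "Baseline of safety laboratory tests is defined as the pre-dose measurement on Day -1". SAP 6.2.2.2 repeats that baseline and describes the output in one sentence: "Laboratory data will be listed and summarized by dose in accordance with the sponsor reporting standards". Neither section names a shift table or a count by baseline status.

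Protocol 5.2, criterion 19, sets the laboratory limits for entry. Total bilirubin excludes at 1.5 times the upper limit of normal (ULN) or more, but "participants with a history of Gilbert's syndrome may have direct bilirubin measured and would be eligible for this study" if direct bilirubin is not above ULN. The other limits cover AST, ALT, haemoglobin, platelets, white cells, neutrophils, lymphocytes and eGFR.

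**The concern.** A count of abnormalities by dose is naturally read as a description of what happened after dosing. If the rule disregards the pre-dose value, a participant who entered with an abnormal result and still has it on Day 3 counts the same as one whose result became abnormal after ritlecitinib. A placebo arm would show the background rate, but both groups here receive the drug (Protocol 4.1). With so few participants, one or two pre-existing abnormalities could look like a drug effect or a dose difference.

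The treatment is also out of line with the rest of the SAP, which uses the pre-dose state for the other safety data:

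- Adverse events that began before the first dose are not treatment-emergent (3.5.1).
- Vital signs and ECG are summarised as change from baseline (6.2.2.3, 6.2.2.4).
- In Appendix 1, blood pressure, QTcF, PR and QRS each have a change category beside the absolute one. The PR change category itself depends on whether baseline exceeded 200 ms.

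**Working it through.** The plan gives no figure to reproduce: the sample size has no statistical derivation and the flag thresholds are not stated. The check is a comparison of sections, followed by simple arithmetic on scale.

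**Can an unchanged value be counted?**

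1. *Which values are assessed.* The SAP sentence does not say post-dose, but that is the reasonable reading. The schedule of activities has safety laboratory tests at screening, Day -1, Day 3 and early termination, so each participant has one scheduled post-dose set.
2. *Total bilirubin.* Without Gilbert's syndrome, values above 1.0 and below 1.5 × ULN are admitted. With it, total bilirubin has no upper limit as long as direct bilirubin is at or below ULN. Suppose such a participant has 2 × ULN on Day -1 and on Day 3. The change is 2 − 2 = 0, yet the participant is counted under any criterion that 2 × ULN satisfies.
3. *Tests without an entry limit.* Protocol Table 4 includes glucose, potassium, uric acid, alkaline phosphatase, albumin and all of urinalysis. Criterion 19 gives no number for any of these. Only the general requirement of good health and the investigator's judgment apply.
4. *Result.* An unchanged value can be counted. Whether it will be depends on the sponsor criteria.

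**How much can one case move the table?**

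Protocol 4.1 plans 8 participants per dose, with at least 6 completing. One participant is 1/8 = 12.5% of an arm of 8, or 1/6 = 16.7% of an arm of 6.

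**How likely is at least one such case?**

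Let p be the proportion of participants who already meet some flag before dosing. The documents do not give p, so a range is assumed. The chance of at least one among n is 1 − (1 − p)^n.

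| Assumed p | n = 8 (one arm) | n = 16 (both arms) |
|---|---|---|
| 2% | 15% | 28% |
| 5% | 34% | 56% |
| 10% | 57% | 82% |
| 20% | 83% | 97% |

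**What share of the count could be pre-existing?**

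Let r be the proportion of pre-existing flags still present on Day 3, and v the rate of new flags among the other participants. The expected count rate is p·r + (1 − p)·v, and the pre-existing share is p·r divided by that sum. With assumed p = 10%, r = 80% and v = 5%:

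- Count rate = 0.10 × 0.80 + 0.90 × 0.05 = 0.080 + 0.045 = 12.5%.
- Pre-existing share = 0.080 / 0.125 = 64%.
- Rate among participants not flagged on Day -1 = 5%.

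With r held at 80%, p from 5% to 20% and v from 5% to 10%, the pre-existing share runs from 30% (p = 5%, v = 10%) to 80% (p = 20%, v = 5%). These figures only illustrate; none of the three rates comes from the documents.

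**The case against.** The strongest reply is that the documents do not show that any admitted value would be flagged. The criteria sit in a sponsor standard that we do not have. If the bilirubin criterion were well above 1.5 × ULN, mildly raised values would never count. The same standard may already contain a table split by baseline. Both points stand, so the finding is that pre-existing abnormalities *can* be counted. A reader might infer that they certainly will be reported as post-dose findings; the documents do not support that.

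A reader might also link the problem to the named risk of a "transient decrease in leukocyte and platelet counts" (Protocol 2.3.1), since entry excludes only white cells at or below 3.0 × 10⁹/L, platelets at or below 100 × 10⁹/L, "or ANC < 1500 cells/mm³ or ALC < 800 cells/mm³". That link is not established. No reference limits or flags for these counts are given. If the lymphocyte flag were assumed to be 0.8 times the lower limit of normal, it would be 0.8 × 1000 = 800 cells/mm³ at a lower limit of 1000. Values below 800 are already excluded, so there is no overlap. Overlap appears only at higher assumed limits: at 1200, for instance, the flag is 960. Nor is this the only drug risk in the protocol: section 2.3 names infection and viral reactivation, and section 4.2.2 names developmental toxicity.

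Other outputs also help. With about 16 participants and one scheduled post-dose sample, the listing should let a reader compare Day -1 with Day 3 for each person. Protocol 10.3.1 lets the investigator treat worsening from baseline as an adverse event. No hypothesis is tested (SAP 5.1) and the plan states no laboratory decision rule. The 12.5-point figure holds for any event in an arm of eight. All of this limits the consequence, but it does not change what the summary count, as written, mixes together.

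**Conclusion.** The point holds in limited form. The laboratory count in SAP 3.5.2 can include abnormalities present before dosing and unchanged since Day -1. The clearest routes are total bilirubin in Gilbert's syndrome and tests with no entry limit. With no untreated arm and about 8 participants per dose, the count by itself cannot tell pre-existing from new.

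A reader might go further and say that the study cannot separate the two. It can, case by case, from the listings and the adverse event record; the gap is in the summary.

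The conclusion assumes that the count refers to post-dose values and that at least some sponsor criteria lie within the range entry allows. The size of the effect is unknown: one participant is worth 12.5 percentage points, and the number of such participants cannot be had from the documents. Only a descriptive secondary safety summary is affected, and target occupancy is untouched. Severity is minor, and this is a cheap improvement.

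**What to change.** In SAP 3.5.2 and 6.2.2.2, keep the existing count, because dropping everyone with an abnormal baseline would hide those who worsen. Then add one of the following by dose:

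- the same count split by Day -1 status: criterion not met on Day -1; criterion met on Day -1 and worse after dosing; or
- a shift table from Day -1 to Day 3 or early termination.

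State in advance what counts as worse for numeric results and for dipstick grades, and show the denominator for each Day -1 group. Base the laboratory safety statement in the study report on abnormalities that are new or worse than Day -1. If the sponsor reporting standard already produces such a table, a sentence in 6.2.2.2 naming it is enough.

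The cost is one small extra table from data already collected. No additional sampling and no protocol amendment are needed.
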